9.1.3 Biopsy

Pre- and post-treatment biopsies will be required for 20 patients in each of the expansion cohorts of UPS and LPS. Mandatory biopsies will be obtained during screening prior to first study drug administration (week 0), and at week 8 (\pm 1 week). Additional optional biopsies of easily accessible tumors may also be performed at cycle 12 (week 34) and at time of progression. Surgical excisional or core biopsies are acceptable. Ten patients whose disease is not amenable to biopsy can be enrolled in each of the expansion cohorts of UPS and LPS and no biopsy will be required.

| | Schedule for Tumor Bio | psy Samples Colle | ction |
|----------------------------------|--|--|--|
| Time points f | or Tumor biopsy samples collection | 20 Patient Cohorts (UPS and LPS) | 10 Patient Cohorts (UPS and LPS) without disease amenable to |
| Archival Tumor Samples | After eligibility is confirmed | Mandatory | Mandatory |
| Mandatory , pre- treatment | After eligibility is confirmed, prior to first study drug administration | Mandatory | |
| Mandatory, on- treatment | At week 8 (+/- 1week) | Mandatory | |
| Optional, cycle 12 | At week 34 (+/- 1week) | Optional | |
| Optional, end of study treatment | At disease progression | Optional | |

Archival tissue will be mandatory for PD-L1 testing on all patients.

Biopsies will be processed for IHC:

1. Evaluation of PD-L1 expression

2. Evaluation of CD8⁺ and CD4⁺ T cell infiltrates.

Biopsies will be processed for single cell suspensions for intracellular cytokine assays:

1. Expression of inhibitory receptors including Tim-3 and BTLA by $\rm CD8^+$ and $\rm CD4^+\,TILs.$

2. Expression of a number of inhibitory ligands including PD-L1, HVEM, and galectin-9 by tumor cells and tumor-infiltrating antigen presenting cells.

10. STUDY EVALUATIONS AND STUDY CALENDAR

10.1 SCREENING STUDIES

The following procedures will be performed during the screening period:

- Informed consent
- History/demographics updated within 2 weeks prior to patient enrollment
- Documentation of sarcoma histology and grade, and prior sarcoma therapies
- Physical exam, including height, weight, vital signs, ECOG performance status
- CBC with differential
- Comprehensive Serum Chemistry Panel
- T3, FT4, and TSH
- PT (or INR) and aPTT
- Urinalysis
- Serum β -HCG or urine pregnancy test for women of childbearing potential
- Archival Formalin Fixed Paraffin Embedded (FFPE) Tumor Samples (on patients enrolled in the expansion cohorts)
- Blood for research studies will be collected (pre-treatment) after eligibility for study is confirmed
- Tumor Biopsy (pre-treatment) after eligibility for study is confirmed.
- Baseline radiologic imaging that is appropriate for the specific histologic subtype per National Comprehensive Cancer Network guidelines for sarcoma (see http://www.nccn.org/professionals/physican_glas/PDF/sarcoma.pdf and http://www.nccn.org/professionals/physican_glas/PDF/sarcoma.pdf and http://www.nccn.org/professionals/physican_gls/PDF/sarcoma.pdf and http://www.nccn.org/professionals/physician_gls/PDF/sarcoma.pdf and http://www.nccn.org/professionals/physician_gls/PDF/sarcoma.pdf and http://www.nccn.org/professionals/physician_gls/PDF/sarcoma.pdf and http://www.nccn.org/professionals/physician_gls/PDF/bone.pdf)
- EKG within 30 days prior to first study drug administration.

The screening period will be up to 30 days prior to first study drug administration (Day1 Cycle1). Laboratory baseline evaluations are to be conducted within 14 days prior to first administration of study drug. Radiologic imaging must be done 30 days prior to first study drug administration

10.2 ON STUDY EVALUATIONS

Patients who have previously met laboratory inclusion criteria at screening may potentially receive Cycle 1 dose of medication even if laboratory studies drawn on

Cycle 1 day one do not meet the eligibility criteria. Study drug may be given as long as labs do not meet threshold for dose delay/schedule modification. Cycle visits will occur at each treatment visit (i.e. every 3 weeks) from study initiation. The following procedures will be performed during the treatment period:

- Physical exam, including weight, vital signs, ECOG performance status
- Administration of study drug
- Recording of adverse events
- Relevant laboratory evaluations, WBC, Hgb, Plt, ANC, Cr, K, Ca, ALT, AST, Total Bilirubin, alkaline phosphatase, PT (or INR), PTT, TSH, Free T4, T3
- Blood for research studies will be collected at week 8 (± 1 week) and then every 12 weeks (± 1 week) subsequently until patient completes 12 cycles
- Disease assessments will be performed at week 8 (± 1 week) and then every 12 weeks (± 1 week) subsequently
- Biopsy at week 8 (\pm 1 week) and optional biopsy may be collected at cycle 12.

NOTE: All studies can be obtained ± 3 days of stated time point unless otherwise noted.

10.3 OFF TREATMENT EVALUATIONS

Final visit is to be performed at the time (or within 30 days +/- 14 days of removal from the treatment). Off treatment evaluations will include:

- Physical exam: height, weight vital signs, ECOG performance status
- Serum β -HCG or urine pregnancy test for women of childbearing potential
- Relevant laboratory evaluations, including CBC with differential and comprehensive serum chemistry panel
- Urinalysis
- PT (or INR) and PTT
- EKG
- Recording of adverse events (for unresolved adverse events, patients should be monitored for 30 days following the last dose of study drug)
- Extent of disease evaluation with appropriate radiographic procedures if not performed within 30 days of the final visit
- Off treatment Biopsy collected due to progression (optional).

Follow-Up:

Patients who complete study treatment should be followed for survival every 6 months. Patient will be contacted by phone at a minimum and survival status will be collected and documented. Survival status can also be assessed via patient's medical records or via certified letter.

STUDY CALENDAR

| | Pre- Study | Wk 1 | Wk 4 | Wk 7 | Wk 10 | Wk 13 | Wk 16 | Wk 19 | Wk 22 | Wk 25 | Wk 28 | Wk 31 | Wk ^K 34+ | Off Treatment ¹ |
|--|----------------|------------------|---------|---------|---------------------|----------|----------|----------|--------------------|----------|----------|---------------|------------------------|-------------------------------|
| Study Drug Admin ^a | | Х | Х | Х | Х | Х | Х | Х | Х | Х | Х | Х | Х | |
| Informed consent | Х | | | | | | | | | | | | | |
| History/Demographics | Х | | | | | | | | | | | | | |
| Physical exam ^b | Х | Х | Х | Х | Х | Х | Х | Х | Х | Х | Х | Х | Х | Х |
| CBC with Differential ^c | X f | Х | Х | Х | Х | Х | Х | Х | Х | Х | Х | Х | Х | Х |
| Comprehensive Serum Chemistry Panel ^d | X f | х | Х | х | Х | Х | Х | Х | Х | Х | Х | Х | Х | Х |
| TSH, FT4, T3 | X f | Х | Х | Х | Х | Х | Х | Х | Х | Х | Х | Х | Х | |
| PT (or INR) and PTT | X f | Х | Х | Х | Х | Х | Х | Х | Х | Х | Х | Х | Х | Х |
| Urinalysis | X f | | | | | | | | | | | | | Х |
| Serum or urine pregnancy test ^e | X f | | | | | | | | | | | | | Х |
| EKG | X g | | | | | | | | | | | | | Х |
| Archival Tumor Samples (FFPE) (only patients from expansion) | Х | | | | | | | | | - | | | | |
| Adverse event evaluation | | Χ- | | | | | | | | | | | X | Х |
| Biopsies | Х | X ^J - | | | | | | | | | | | X ^J | Х |
| Radiologic evaluation | X ^h | First | radiolo | ogic m | easurem | | | | ied at 8 bseque | | (± 1 w | eek) initiall | y, then | X ⁱ |
| Blood Sample Collection | X ^m | | | | l be col tion wi | | | | | | | 1 week), w | eek 32 | |
| Follow up | | | | | | | | | | | | | | X ⁿ |

a: Pembrolizumab

b: Including height, weight ,vital signs, ECOG performance status

c: WBC, Hgb, Plt, ANC, PT (or INR), PTT

d:Cr, K, Ca, ALT, AST, Alkaline phosphatase, Total bilirubin

e: Women of childbearing potential

f: Laboratory baseline evaluations are to be conducted within 14 days prior to first study drug dose

g:EKG within 30 days prior to first study drug administration

h: Scans and x-rays must be performed within 30 days prior to first study drug dose

i: Extent of disease evaluation with appropriate radiographic procedures if not performed within 30 days of the final visit. j: Mandatory biopsies will be collected pre and post treatment at week 0 and 8 and optional biopsies may be collected at cycle 12 (week 34) and at time of progression for 20 patients enrolled in the expansion cohorts of UPS and LPS.

k: Patients may continue on study drug beyond 12 cycles at discretion of study doctor. Use monthly visits as a template for every monthly evaluations as long as patient remains on study drug.

1: Off-study evaluation should be performed at the time (or within 30 days) of removal from study.

m: Blood samples will be collected pre-treatment (after eligibility is confirmed)

n: Patient will be followed for survival every 6 months via phone call at a minimum. Survival status will be documented after each call.

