5.7 Duration of Follow Up

Patients will be followed for 30 days +/- 14 days after termination of study treatment or until death, whichever occurs first. Patients removed from study for adverse event(s) will be followed until resolution or stabilization of the adverse event.

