7.2 Handling of Safety Parameters

7.2.1 Reporting of Adverse Events

All adverse events (related and unrelated) grade 1-5 occurring during the study and up to 30 days after the last dose of study medication must be reported and recorded in the study database. Reporting the specific time of onset of a given AE is only necessary when it occurs in relation to study drug administration.

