7.2.2 Reporting of Serious Adverse Events (immediately reportable)

Any clinical adverse event or abnormal laboratory test value that is *serious* and which occurs during the course of the study (as defined in section 7.1.3below), must be reported to SARC **within** *24 hours* of the site investigator becoming aware of the event. If only limited information is initially available, follow-up reports are required. The original SAE form must be kept on file at the study site.

SAEs must be reported on the MedWatch Form 3500A along with the completed Fax/Email Coversheet and faxed or emailed to SARC office (See Appendix B). SARC will notify Merck within 1 working day by faxing the complete report to:

Merck Global Safety Attn: Worldwide Product Safety [contact]

Related Serious Adverse Events *MUST* be collected and reported regardless of the time elapsed from the last study drug administration, even if the study has been closed.

Unrelated Serious Adverse Events must be collected and reported during the study and for up to 30 days after the last dose of study medication

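### The last visit that records adverse events may fall before the 30-day reporting window closes, and no later scheduled contact asks about new events

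*Combined protocol and SAP*

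**What the plan says.** Four passages set the timing, and each counts from a different date.

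- **Section 7.2.1** (from the last dose): adverse events of grades 1 to 5, related or not, "occurring during the study and up to 30 days after the last dose of study medication must be reported and recorded in the study database".
- **Section 10.3** (from removal from treatment): "Final visit is to be performed at the time (or within 30 days +/- 14 days of removal from the treatment". Recording of adverse events is among the procedures listed for this visit.
- **Study Calendar, footnote to the Off Treatment column** (from removal from study): "Off-study evaluation should be performed at the time (or within 30 days) of removal from study". The 14-day tolerance of 10.3 is absent here.
- **Section 5.7** (from termination of treatment): "Patients will be followed for 30 days +/- 14 days after termination of study treatment or until death, whichever occurs first".

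Two provisions extend contact for events that are already known. Section 10.3 adds that "for unresolved adverse events, patients should be monitored for 30 days following the last dose of study drug", and section 5.7 that "Patients removed from study for adverse event(s) will be followed until resolution or stabilization of the adverse event". Section 7.1.1.6 likewise sets out how long identified events are followed. After the final visit, 10.3 and the calendar schedule contact every six months, and only survival status is collected then.

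**The concern.** The reporting window is fixed by the last dose, whereas the visit that should fill it is fixed by removal and may be held on that same day. A site can keep to the visit schedule and still have no planned occasion to ask about events that begin between that visit and day 30. The provisions for unresolved events do not help, because a new event is not yet on anyone's list.

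Safety and tolerability are secondary objective 1, and 13.4.1 puts special emphasis on immune-related events. Section 6.2 itself notes that such events can appear several months after the last dose. If the query date depends on when the visit is booked, the length of the window actually covered can differ between patients and sites.

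Early removal is an ordinary route off this trial. The planning PFS rates of 20% and 40% (at four months in the synopsis, three months in 13.3) imply that 60% to 80% of patients will have progressed or died by then. Progression is a listed reason to stop in 5.6, although treatment beyond progression is allowed when there is clinical benefit.

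**Working it through.** The plan states no figure for this point, so there is none to reproduce. The check is day arithmetic.

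**Inputs from the protocol**
- Reporting window: 30 days from the last dose (7.2.1).
- Earliest final visit: 0 days after removal (10.3 and the calendar footnote).
- Follow-up under 5.7: 30 − 14 = 16 days to 30 + 14 = 44 days after termination.
- Cycle length: 21 days (2.17), with ±3 days for dosing after cycle 1 (5.2).
- Scans: week 8 ±1 week after treatment starts, then every 12 weeks ±1 week (2.17).

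**Assumption.** The documents do not fix the lag from last dose to removal, so it is varied. Removal from treatment, removal from study and termination are taken as the same day.

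**Formula.** Uncovered days = max(0, 30 − (lag + offset)), where the offset is the number of days from removal to the last contact that asks about adverse events.

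**Lag at a scheduled scan.** With doses on days 1, 22 and 43, the week-8 scan falls on day 1 + 56 = 57, which is 57 − 43 = 14 days after the third dose. The ±7-day scan window gives 7 to 21 days. Later scans are 84 days apart, exactly four 21-day cycles, so on undelayed dosing each also falls 14 days after a dose.

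**Lag at the next dosing visit.** 21 days, or 18 to 24 with the ±3-day window.

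| Lag (days) | Situation | Uncovered, visit on day of removal | Uncovered, last contact 16 days later |
|---|---|---|---|
| 0 | removal on a dosing day, after the dose | 30 | 14 |
| 7 | scan at its earliest | 23 | 7 |
| 14 | scan on schedule | 16 | 0 |
| 18 | next dosing visit, 3 days early | 12 | 0 |
| 21 | next dosing visit, or scan at its latest | 9 | 0 |
| 24 | next dosing visit, 3 days late | 6 | 0 |
| 30 or more | for example after a long toxicity hold | 0 | 0 |

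The day-of-removal option therefore leaves a gap whenever the lag is under 30 days. The 16-day option leaves one only when the lag is under 30 − 16 = 14 days. A contact 30 to 44 days after removal leaves none at any lag.

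**Share of the whole adverse-event window.** For the three-dose patient the window runs from day 1 to day 43 + 30 = 73, a length of 72 days. Removal and final visit at the week-8 scan leave 16/72 = 22% uncovered (9/72 = 12.5% to 23/72 = 32%).

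**Whether another scheduled contact fills the gap.** The 30-day monitoring in 10.3, the extended follow-up in 5.7 and the rules in 7.1.1.6 all start from an event already identified. The six-monthly contact asks about survival. None asks about new events.

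**The case against.** The strongest reply is that 7.2.1 binds whatever the visit date. A site that learns of a new event on day 25 must record it, and a site that records nothing after an early visit has not met 7.2.1. For serious events, 7.2.2 says "Unrelated Serious Adverse Events must be collected and reported during the study and for up to 30 days after the last dose of study medication", sets no time limit for related ones, and 7.2.5 adds its own post-treatment duty. That stands, and it confines the exposure largely to new-onset, non-serious events. It does not remove the exposure, since a duty to record does not bring out a minor event from a patient whom nobody is due to contact.

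Second, 5.7 is a separate duty. Read together with 10.3, follow-up runs to at least day 16 after termination even if the examination is done on the day of removal, and the gap is then zero for any lag of 14 days or more. This is a fair reading, but 5.7 does not say what the follow-up consists of or that new adverse events are asked about, so it cannot be relied on to close the gap.

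Third, patients removed because of an adverse event stay in contact until it resolves or stabilizes. This also stands, and makes the shortest lags less worrying.

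Fourth, this is an open-label trial in which everyone receives pembrolizumab, so no treatment comparison is biased. The documents do not say when sites book the visit, so uneven capture between sites is possible but not shown.

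A reader might infer that events in the window are never asked about, or that as much as 30/72 = 42% of a three-dose patient's window is lost. The documents do not support either as a general statement. Later visits are expressly allowed. The 42% needs removal and the final visit both to fall on the day of the third dose, after dosing, yet 5.2 places the day's assessments before the infusion.

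**Conclusion.** The point holds in limited form. The permitted visit timing can leave part of the protocol's own adverse-event window without any scheduled query for new events, and the four passages disagree on the reference date.

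In the two most ordinary situations, a day-of-removal visit leaves about 16 days (removal at a scan) or about 9 days (removal at the next dosing visit) of the 30 uncovered. If 5.7 is taken to guarantee an adverse-event query at its earliest limit, the gap is at most 7 days for removal at a scan and zero at the next dosing visit. These sizes assume undelayed dosing and use of the earliest permitted contact. How often sites do that is unknown.

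The consequence is possible under-capture of late, new-onset, non-serious events for secondary objective 1. Response rate, PFS and OS are untouched. It is a worthwhile, inexpensive improvement and does not threaten the trial's conclusions.

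**What to change.** Reconcile 5.7, 10.3 and the Off Treatment footnote with 7.2.1 on one stated reference date, and give 10.3 and the footnote the same tolerance. Add one sentence that adverse events are queried once at or after the end of the 7.2.1 window. Where the final visit falls earlier, the query can be made by phone or from the medical record, methods that 10.3 already uses for survival status.

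The final visit can stay where sites now hold it. The change concerns data collection only and touches no dosing, stopping or event-management rule. The cost is wording in three places and one short extra contact for patients whose final visit precedes the end of the window.

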11. MEASUREMENT OF EFFECT

11.1 Antitumor Effect – Solid Tumors

For the purposes of this study, patients should be evaluated for response initially after first 8 weeks on study and then every 12 weeks.

Response and progression will be evaluated in this study using the new international criteria proposed by the revised Response Evaluation Criteria in Solid Tumors (RECIST) guideline (version 1.1) [*Eur J Ca* 45:228-247, 2009]. Changes in the largest diameter (unidimensional measurement) of the tumor lesions and the shortest diameter in the case of malignant lymph nodes are used in the RECIST criteria.

11.1.1 Definitions

Evaluable for toxicity. All patients will be evaluable for toxicity from the time of their first treatment with pembrolizumab.

Evaluable for objective response. Only those patients who have measurable disease present at baseline, have received at least one cycle of therapy, and have had their disease re-evaluated will be considered evaluable for response. These patients will have their response classified according to the definitions stated below. (Note: Patients who exhibit objective disease progression prior to the end of cycle 1 will also be considered evaluable.)

11.1.2 Disease Parameters

Measurable disease. Measurable lesions are defined as those that can be accurately measured in at least one dimension (longest diameter to be recorded) as ≥ 20 mm by chest x-ray or as ≥ 10 mm with CT scan, MRI, or calipers by clinical exam. All tumor measurements must be recorded in millimeters (or decimal fractions of centimeters).

Note: Tumor lesions that are situated in a previously irradiated area are not considered measurable unless there is evidence of progression after radiation therapy.

Malignant lymph nodes. To be considered pathologically enlarged and measurable, a lymph node must be \geq 15 mm in short axis when assessed by CT scan (CT scan slice thickness recommended to be no greater than 5 mm). At baseline and in follow-up, only the short axis will be measured and followed.

Non-measurable disease. All other lesions (or sites of disease), including small lesions (longest diameter < 10 mm or pathological lymph nodes with \ge 10 to < 15

mm short axis), are considered non-measurable disease. Bone lesions, leptomeningeal disease, ascites, pleural/pericardial effusions, lymphangitis cutis/pulmonitis, inflammatory breast disease, and abdominal masses (not followed by CT or MRI), are considered as non-measurable.

Note: Cystic lesions that meet the criteria for radiographically defined simple cysts should not be considered as malignant lesions (neither measurable nor non-measurable) since they are, by definition, simple cysts.

'Cystic lesions' thought to represent cystic metastases can be considered as measurable lesions, if they meet the definition of measurability described above. However, if non-cystic lesions are present in the same patient, these are preferred for selection as target lesions.

Target lesions. All measurable lesions up to a maximum of 2 lesions per organ and 5 lesions in total, representative of all involved organs, should be identified as **target lesions** and recorded and measured at baseline. Target lesions should be selected on the basis of their size (lesions with the longest diameter), be representative of all involved organs, but in addition should be those that lend themselves to reproducible repeated measurements. It may be the case that, on occasion, the largest lesion does not lend itself to reproducible measurement in which circumstance the next largest lesion which can be measured reproducibly should be selected. A sum of the diameters (longest for non-nodal lesions, short axis for nodal lesions) for all target lesions will be calculated and reported as the baseline sum diameters. If lymph nodes are to be included in the sum, then only the short axis is added into the sum. The baseline sum diameters will be used as reference to further characterize any objective tumor regression in the measurable dimension of the disease.

Non-target lesions. All other lesions (or sites of disease) including any measurable lesions over and above the 5 target lesions should be identified as **non-target lesions** and should also be recorded at baseline. Measurements of these lesions are not required, but the presence, absence, or in rare cases unequivocal progression of each should be noted throughout follow-up.

